#### **4.4.2 Main Analytical Approach**

All analysis of secondary endpoints will be presented for FAS, unless specified otherwise.

##### **4.4.2.1 DOR per IRC**

Number and percentage of participants with event and each event type (death, PD), censoring and each censoring type (no event, start new anti-cancer treatment before PD or death) will be summarized. DOR will be analyzed using Kaplan-Meier methodology and Kaplan-Meier plots will be provided. The median DOR and its two-sided 95% CI will be calculated.

In addition, the DOR rate at 6 and 12 months will be summarized along with 95% CI. The DOR at 6 and 12 months is defined as the proportion of the responders who are still ongoing response after 6 and 12 months from their first documented response.

##### **4.4.2.2 DCR per IRC**

DCR will be summarized and the exact 2-sided 95% CI will be calculated using the Clopper-Pearson method.

##### **4.4.2.3 PFS per IRC**

Number and percentage of participants with event and each event type (death, PD), censoring and each censoring type (no event, start new anti-cancer treatment before PD or death) will be summarized. PFS per IRC will be analyzed using Kaplan-Meier methodology and Kaplan-Meier plots will be provided. The median PFS and its two-sided 95% CI will be calculated. In addition, the 6- and 12-month PFS rates will be summarized along with the corresponding 95% CI.

##### **4.4.2.4 Confirmed ORR per Investigator Assessment**

The exact 2-sided 95% CI will be calculated for the confirmed ORR per investigator.

Time to response per investigator will be analyzed in the same way as the time to response per IRC.

##### **4.4.2.5 Concordance between Investigator and IRC Assessment**

A summary of the concordance between investigator and IRC assessment will be provided. The percent agreement will be calculated as the proportion of participants whose best overall response per IRC match the best overall response per investigator. Percent agreement =  $(\text{Number of matched responders} + \text{Number of matched non-responders}) / \text{Total number of participants assessed}$ .

#### **4.4.2.6 DOR per Investigator Assessment**

DOR per investigator will be analyzed in the same way as the DOR per IRC.

#### **4.4.2.7 DCR per Investigator Assessment**

DCR per investigator will be analyzed in the same way as the DCR per IRC.

#### **4.4.2.8 PFS per Investigator Assessment**

PFS per investigator will be analyzed in the same way as the PFS per IRC.

#### **4.4.2.9 Overall Survival**

Number of participants with event and censoring will be summarized. OS will be analyzed using Kaplan-Meier methodology and Kaplan-Meier plots will be provided. The median OS and its two-sided 95% CI will be calculated. The OS rates at 6 and 12 months will be summarized along with the corresponding 95% CI.

#### **4.4.2.10 Tumor Shrinkage per IRC**

The maximum percent reduction from baseline in the sum of diameters (longest diameter for non-nodal lesions and short axis for nodal lesions) in target lesion(s) per IRC will be calculated for each participant with both baseline and at least 1 post-baseline measurements and presented graphically with a waterfall plot. The percent change from baseline for each participant at each assessment will be presented with a spider plot.

#### **4.4.2.11 Tumor Shrinkage per Investigator Assessment**

Tumor shrinkage per investigator will be analyzed in the same way as the tumor shrinkage per IRC.

### **4.4.3 Sensitivity Analysis**

The following sensitivity analysis will be performed for the DOR per IRC:

1. A sensitivity analysis to censor participants who progressed or died after an extended loss to follow up (i.e.,  $\geq 2$  consecutive missed response assessments) at the date of the last adequate response assessment prior to the missed visits.

The following sensitivity analysis will be performed for the PFS per IRC:

1. A sensitivity analysis to censor participants who progressed or died after an extended loss to follow up (i.e.,  $\geq 2$  consecutive missed response assessments) at the date of the last adequate response assessment prior to the missed visits.

### **4.5 Analysis of Safety**

Safety endpoints are secondary endpoints in this study. The SAF will be used for the safety analysis.

Safety endpoints include AEs, laboratory tests, vital signs, ECGs and ECOG performance status. Safety will be assessed by evaluation of the following variables:

- Treatment-emergent adverse events (TEAEs; frequency, severity, seriousness, and relationship to study drug).
  - TEAE is defined as an adverse event observed after starting administration of the study drug and within 30 days after taking the last dose of study drug. If the adverse event occurs on the first dosing date and the onset check box is marked “Onset after first dose of study drug” or the onset check box is left blank, then the adverse event will be considered treatment emergent. If the adverse event occurs on the first dosing date and the onset check box is marked “Onset before first dose of study drug”, then the adverse event will not be considered treatment emergent. If a participant experiences an event both during the pre investigational period and during the investigational period, the event will be considered as TEAE only if it has worsened in severity (i.e., it is reported with a new start date). If a complete onset date is unknown, and the onset check box is marked “Onset after first study drug taken”, then the adverse events will be considered treatment emergent. If the onset check box is marked “Onset before study drug taken”, then the adverse event will not be considered treatment emergent. If onset check box is left blank, imputed onset date as specified in Section 4.11.2 will be used to determine whether an adverse event is treatment emergent.
  - A drug-related TEAE is defined as any TEAE with relationship “yes” to study treatment as assessed by the investigator or with missing assessment of the causal relationship.
- Serious adverse events (SAEs) include adverse events that are flagged as serious by the investigator on eCRF or the SAE flag by the investigator on CRF is missing, or upgraded by the Sponsor based on review of the Sponsor’s list of Important Medical Events.
- Adverse events of special interest
  - Peripheral neuropathy, corneal disorders and blurred vision, dry eye, hyperglycemia, skin reactions, and infusion related reactions (IRR) are considered adverse events of special interest (AESI) for enfortumab vedotin. These are medical concepts of composite terms based on the search criteria (standard MedDRA query [SMQ] or sponsor specified query [SSQ]). Other AEs may be added to AESI as necessary. The search criteria for AESI will be maintained in a separate document and finalized prior to final database lock.
  - For selected AESI, time to onset of AESI will be calculated.

Time to onset of a specific AESI will be calculated as time from the first dose of study drug to the start of first treatment-emergent event that meets the respective search criteria.

Time to onset is defined at the participant level.
- Clinical laboratory variables

Below is a table of the laboratory tests that will be performed during the conduct of the study. Refer to the Schedule of Assessments in the protocol for study visit collection dates.

## Laboratory Assessments

Panel/Assessments	Parameters to be Analyzed
Hematology	Hematocrit Hemoglobin Platelets Red blood cell count White blood cell count White blood cell count differential
Biochemistry	Albumin Alanine aminotransferase Alkaline phosphatase Aspartate aminotransferase Bicarbonate Blood urea Blood urea nitrogen Calcium Chloride Creatinine Hemoglobin A1c (HbA1c, screening and EOT only) High density lipoprotein (HDL) (Screening only) Glucose a Lactate dehydrogenase Low-density lipoprotein (LDL) (Screening only) Magnesium Phosphate Potassium Serum HCG for female participants Sodium Total and direct bilirubin Total cholesterol (Screening only) Total protein Triglyceride (Screening only)
Urinalysis	Specific gravity pH Blood Protein Glucose Bilirubin Microscopic (epithelial cells, bacteria, casts, crystals, WBC and RBC)
Serology	Hepatitis B and C at screening

EOT: end of treatment; HbA1c: hemoglobin A1c; HCG: human chorionic gonadotropin

a. Glucose at screening and on Cycle 1 Day 8 are required to be tested in fasting status in order to ensure accurate interpretation of glucose values. Fasting is not necessary for biochemistry laboratory tests performed at all other visits.

- Vital signs (systolic and diastolic blood pressures (mmHg), radial pulse rate (beats/minute) and body temperature (C) and weight
- 12-lead electrocardiogram (ECG)
- ECOG performance scores

#### **4.5.1 Adverse Events**

All adverse event (AE) recorded on treatment including within 30 days from the last study treatment will be summarized.

The coding dictionary for this study will be MedDRA. It will be used to summarize AEs by SOC and PT. AEs will be graded using National Cancer Institute's Common Terminology Criteria for AEs (NCI-CTCAE, Version 4.03).

An overview table will include the following details by treatment group and overall:

- Number and percentage of participants with TEAEs,
- Number and percentage of participants with causally drug-related TEAEs,
- Number and percentage of participants with serious TEAEs and Astellas upgraded serious TEAE,
- Number and percentage of participants with serious drug-related TEAEs and Astellas upgraded serious drug-related TEAE,
- Number and percentage of participants with TEAEs leading to permanent discontinuation of study drug,
- Number and percentage of participants with drug-related TEAEs leading to permanent discontinuation of study drug,
- Number and percentage of participants with grade 3 or higher TEAE
- Number and percentage of participants with grade 3 or higher drug-related TEAE
- Number and percentage of participants with TEAEs leading to dose reduction,
- Number and percentage of participants with drug-related TEAEs leading to dose reduction,
- Number and percentage of participants with TEAEs leading to drug interruption,
- Number and percentage of participants with drug-related TEAEs leading to drug interruption,
- Number and percentage of participants with TEAEs leading to death,
- Number and percentage of participants with drug-related TEAEs leading to death
- Number and percentage of participants with TEAEs leading to death excluding disease progression,
- Number and percentage of participants with drug-related TEAEs leading to death excluding disease progression, and
- Number of deaths

The above overview table will be repeated to report the number of events (all TEAEs which may include multiple events of the same preferred term with the same or different CTCAE grades) and the number of events adjusted by patient year (defined as the total duration of exposure in years).

The number and percentage of participants with TEAEs, as classified by SOC and PT will be summarized by treatment group and overall. Summaries will be provided for:

- TEAEs
- Drug-related TEAEs,

- serious TEAEs and Astellas upgraded serious TEAE,
- drug-related serious TEAEs and drug-related Astellas upgraded serious TEAE,
- TEAEs leading to permanent discontinuation of study drug,
- Drug-related TEAEs leading to permanent discontinuation of study drug,
- TEAEs leading to dose reduction,
- Drug-related TEAEs leading to dose reduction,
- TEAEs leading to drug interruption,
- Drug-related TEAEs leading to drug interruption,
- TEAEs leading to death
- Drug-related TEAEs leading to death
- TEAEs leading to death excluding disease progression
- Drug-related TEAEs leading to death excluding disease progression
- grade 3 or higher TEAEs
- grade 3 or higher drug-related TEAEs
- TEAEs excluding serious adverse events that equal to or exceed a threshold of 5% in any dose level

AE summary tables will include participant counts as opposed to AE counts. If a participant experiences more than one episode of a particular AE, that participant will be counted only once for that event. If a participant has more than one AE that code to the same preferred term, the participant will be counted only once for that preferred term. Similarly, if a participant has more than one AE within a body system, the participant will be counted only once in that body system.

TEAEs and the number and percentage of participants with TEAEs, as classified by SOC and PT will also be summarized by NCI-CTCAE severity grade and by relationship to study drug. If an adverse event changes in severity grade or relationship, then the participant will be counted only once with the worst severity grade and highest degree of relationship. The adverse event however will be presented in each category they were classified to. If a participant has an event more than once with missing severity grade and with non-missing severity grade, then the participant will be counted as the highest non-missing grade. If a participant has an event more than once with missing relationship and with non-missing relationship, then the participant will be counted as relationship=Yes. Drug-related TEAEs will be presented in a similar way by severity only.

The number and percentage of subjects with treatment-emergent adverse events of interest (AESI) as classified by SSQ/CMQ or SMQ and PT will be summarized. For selected AESI, time to onset will be summarized at the participant level. All AEs, deaths, SAEs and withdrawals due to adverse events will be displayed in listings.

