7.3 Adverse Events and Other Safety Aspects

The definitions of an AE or SAE can be found in [Sections 10.3.1 and 10.3.2], respectively.

AEs will be reported by the participant (or, when appropriate, by a caregiver, surrogate, or the participant's legally authorized representative).

The investigator and any qualified designees are responsible for detecting, documenting and recording events that meet the definition of an AE or SAE and remain responsible for following up AEs that are serious, considered related to the study drug, or that caused the participant to discontinue the study drug and/or study (see [Section 10.3 Appendix 3: Adverse Events: Definitions and Procedures for Recording, Evaluating, Follow-up and Reporting]).

The method of recording, evaluating, and assessing causality of AE and SAE and the procedures for completing and transmitting SAE reports are provided in [Section 10.3 Appendix 3: Adverse Events: Definitions and Procedures for Recording, Evaluating, Follow-up and Reporting].

7.3.1 Time Period and Frequency for Collecting Adverse Event and Serious Adverse Event Information

All SAEs will be collected from the signing of the ICF until 30 days following the last dose of study treatment or until initiation of a new anticancer treatment, whichever occurs first, at the time points specified in the schedule of assessments [Section 1.3] and reported on the eCRF.

All AEs will be collected from the signing of the ICF until the follow up visit at the time points specified in the schedule of assessments [Section 1.3] and reported on the eCRF.

If the NCI-CTCAE grade of an SAE/AE changes, the event should be relisted on the eCRF with the new NCI-CTCAE grade and new onset date.

If the NCI-CTCAE grade decreases, the SAE/AE should be relisted on the eCRF with the new NCI-CTCAE grade and new onset date. The exception is ongoing pre-dose events that continue post-dose and improve post-dose. Such events should not be re-listed.

If the NCI-CTCAE grade of an SAE reduces, the details of the AE should be provided on the SAE worksheet for the medical assessor to be able to assess the course of the event.

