## 5 REVISION AND RATIONALE

Version	Date	Changes	Comment/rationale for change
1.0	20-JUL-2021	NA	Original Version
2.0	14-Mar-2022	Section 4.2.11 Extent of Exposure Clarified the definition of duration of exposure, when it was analyzed as a single parameter and when it was used in calculating dose intensity, respectively.	When calculating duration as a single parameter, apply datacut if there is one, however when calculating dose intensity, do not apply datacut, use the “initial dose of last cycle +28-1” rule. The reason is that if the cutoff date is applied, the calculated relative dose intensity almost always exceed 1 under perfect compliance, which may cause confusion.
	14-Mar-2022	Section 4.5.1 Adverse Events 1. Updated AESI terms per EV AESI list version 8 2. Removed the analysis of time to improvement and resolution of AESI	1. AESI list was updated from v7 to v8 2. Analysis of time to improvement and resolution are removed because per current CRF design it is difficult to identify records from the same event to allow performing this type of analysis.
	14-Mar-2022	Section 4.8.1 Analysis of Immunogenicity Revised the definition and analysis of ATA	Clarify the definition and analysis of ATA.
	14-Mar-2022	Section 4.7.1 Subgroup Analyses Removed subgroup analysis for safety endpoints.	Removed considering such analyses would be not that informative based on current relative small sample size and single-arm design.
	10-Jun-2022	Changed all “subject” to “participant”	Per newly updated company level standard term
	10-Jun-2022	Section 4.3.2 Main Analytical Approach. For the analysis of time to response, add a swimmer plot	Use swimmer plot to visualize all participants’ time to response and duration of response.
	10-Jun-2022	Section 4.4.1 Definition of secondary endpoint. Regarding the definition of censoring rule of DOR, remove the sentence of censoring at the date of first CR/PR if no subsequent post-baseline radiological assessment is available	This sentence is not applicable to DOR since only confirmed responders are included in the analysis.
	10-Jun-2022	Section 4.4.2.5. Add concordance analysis between ORR per IRC and per investigator assessment	Add concordance analysis to show discrepancy between ORR per IRC and per investigator assessment.

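### The event-count version of the TEAE overview table counts one continuous episode once per grade step, so stepwise recovery raises the all-TEAE count and the rate per patient-year

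*SAP*

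**What the plan says.** **Recording.** Under Protocol 7.3.1, when the CTCAE grade of an AE or SAE changes, "the event should be relisted on the eCRF with the new NCI-CTCAE grade and new onset date". Improvement is covered in so many words: "If the NCI-CTCAE grade decreases, the SAE/AE should be relisted on the eCRF with the new NCI-CTCAE grade and new onset date". There is one exemption: "The exception is ongoing pre-dose events that continue post-dose and improve post-dose. Such events should not be re-listed".

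**TEAE definition.** SAP 4.5 defines a TEAE as "an adverse event observed after starting administration of the study drug and within 30 days" of the last dose. A relisted record with its onset date in that window meets the definition.

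**Counting.** SAP 4.5.1 first presents the overview table as participants and percentages. It then repeats the table as number of events and as events per patient-year, with total exposure in years as the denominator. The events counted are "all TEAEs which may include multiple events of the same preferred term with the same or different CTCAE grades". The SAP contains no rule that joins relisted records into one event.

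**Linkage.** The revision history in SAP section 5 removes time to improvement and resolution of AESIs because "per current CRF design it is difficult to identify records from the same event to allow performing this type of analysis".

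**The concern.** A table headed number of events, with a rate per patient-year beside it, will be read as how often toxicity occurred. Under these two rules the all-TEAE row also counts how often grades changed. The distortion has an awkward direction: of two participants with the same peak grade, the one who improves stepwise contributes more events than the one who stays at the peak.

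Such paths are to be expected here. Protocol Table 8 has dosing withheld for Grade 2 neuropathy or corneal events until Grade 1 or baseline and then resumed, so a 1-2-1 course is an ordinary one.

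The table also carries some weight. SAP section 5 justifies dropping a separate dose-reduction summary partly because the information already appears in the event-number table. Protocol 2.1 describes the study as a bridge meant to show safety consistent with the non-Chinese population. A rate per patient-year invites comparison across studies, and its value depends on a record-counting convention that the table does not explain. The sponsor removed one AESI analysis because records of one event are hard to link, yet kept an event count that meets the same obstacle.

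**Working it through.** The documents state no event count or rate, so there is no planned figure to reproduce. The check applies the recording rule to grade paths and then looks at the effect on a rate.

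**Step 1. Records per episode.** Rule from Protocol 7.3.1: one record at onset and one at each later change to a non-zero grade. Resolution closes a record and opens none. All onsets are taken to lie in the TEAE window.

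| Grade path of one episode | Episodes | Records counted | Records at Grade 3 or higher |
|---|---|---|---|
| 3, never improves | 1 | 1 | 1 |
| 3, resolves directly | 1 | 1 | 1 |
| 3-2-1, resolves | 1 | 3 | 1 |
| 1-2-3, no recovery | 1 | 3 | 1 |
| 1-2-3-2-1, resolves | 1 | 5 | 1 |
| 3-4-3-2-1, resolves | 1 | 5 | 3 |

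The first and third rows show the problem: same onset grade and same peak, but 1 event without improvement and 3 with it. Comparing 1-2-3 without recovery (3) with 1-2-3-2-1 (5), recovery alone adds 2.

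**Step 2. Which rows of the table.**
- All TEAEs: every record counts, so the row is affected.
- Grade 3 or higher: improvement adds a record only on a step such as Grade 4 to Grade 3, as in the last path.
- Serious, drug-related and action-taken: this depends on whether the flag is carried to the relisted record, which neither document states.

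**Step 3. Does the exemption help?** It covers events ongoing before the first dose that improve afterwards. SAP 4.5 counts a pre-existing event as a TEAE only if it worsens, so the exempt events are generally not TEAEs. The exemption leaves the TEAE count largely as it was.

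**Step 4. Scale, with assumed inputs.** From the documents: up to 40 participants (SAP 4.10) and about 8 months of treatment (Protocol 1.1), giving 40 × 8/12 = 26.7 patient-years. Assumed: 5 TEAE episodes per participant, so 40 × 5 = 200 episodes. A share *s* of episodes improves through *k* extra non-zero grades.

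Rate = 200 × (1 + *s* × *k*) / 26.7. With *s* = 0 this is 200 / 26.7 = 7.5 per patient-year, the rate by episode.

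| Share *s* | *k* = 1 | *k* = 2 |
|---|---|---|
| 25% | 250 / 26.7 = 9.4 | 300 / 26.7 = 11.3 |
| 50% | 300 / 26.7 = 11.3 | 400 / 26.7 = 15.0 |
| 100% | 400 / 26.7 = 15.0 | 600 / 26.7 = 22.5 |

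The inflation factor is 1 + *s* × *k*, from 1.25 to 3 over this grid. It does not depend on the assumed number of episodes or on exposure. It depends on *s* and *k*, which the documents do not give.

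**The case against.** The SAP does disclose that its count may include the same term at different grades, and its severity tables likewise show an event under each grade it reached. Counting records is a recognised convention. Safety is a secondary, descriptive endpoint in a single-arm study; no success criterion uses the rate, and any error overstates toxicity and does not hide it. Protocol 9.4.3.1 plans its TEAE summaries as numbers and percentages of participants, and those are sound.

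Most of this stands and limits the weight of the point. It does not remove it: the disclosure does not tell the reader that one unbroken episode is split into several events, or that improving adds to the total.

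Three stronger readings are tempting, and the documents do not support them.
- **That reported neuropathy or other AESI rates are inflated.** Only the overview table is repeated as event counts and rates, and it has no preferred-term or AESI row. The SOC, preferred-term and AESI tables count participants.
- **That every step of recovery adds an event.** Direct resolution adds none, and an onset more than 30 days after the last dose is not a TEAE. Collection stops earlier still if new anticancer treatment starts (Protocol Table 1, note m). Long up-and-down neuropathy cycles through Grade 3 are also a poor example, because Table 8 has treatment discontinued at Grade 3 neuropathy.
- **That one serious event will be reported as several serious TEAEs.** Protocol 7.3.1 asks for details on the SAE worksheet when an SAE's grade falls. It does not say whether the relisted record keeps the seriousness flag.

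**Conclusion.** The point holds for the event-count and per-patient-year version of the overview table. In its all-TEAE row, one continuous episode counts once per non-zero grade step in the TEAE window, so stepwise improvement raises both the count and the rate. This follows from two stated rules and the absence of a merging rule. It assumes that the SAP's events are the eCRF records. The SAP does not use that word, but its definition and its remark on the CRF leave no other workable reading.

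Other rows may be affected, depending on how flags are carried. Participant counts and percentages, worst-grade participant tables and time to first onset are not affected, and neither is any efficacy result. The size in this trial is unknown; the 1.25- to 3-fold range is an illustration under assumed shares and steps. The change is worth making before database lock, because a rate that rises with recovery should not be reported as an event rate.

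**What to change.** In SAP 4.5.1, define the unit for the event-count and per-patient-year table:

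- Merge records of the same preferred term in one participant into one event when their dates abut (the next record starts on the stop date or the day after) or overlap.
- Apply this after the imputation in SAP 4.11.2, and treat an open stop date as overlapping later records. A rule limited to exactly abutting dates would miss cases: partial stop dates move to the end of the month or year, partial start dates often move to the first of the month, and a missing stop date means ongoing.
- Give the merged event the first onset date, the worst grade, and the most severe seriousness, relationship and action.

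The sponsor has said that "per current CRF design it is difficult to identify records from the same event", so the merge should be tried on the data before it is relied on. If linkage proves unreliable, label the table 'number of AE records (a new record at each grade change)' and drop the rate per patient-year.

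Cost: one SAP paragraph and a little programming, with no new data collection. Some truly separate episodes with touching, imputed or open dates will be merged, so the merged count may be slightly low. The fallback needs only a label change and loses the rate.

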#### **4.2.11 Extent of Exposure**

The following information on drug exposure will be presented by treatment group for the SAF:

- Descriptive statistics for duration of exposure (months), number of cycles, number of infusions per participant, cumulative dose, planned dose intensity, dose intensity and relative dose intensity.
- Number and percent of participants with dose adjustment and reasons for dose adjustment.
- Number and percentage of participants who were treated at each cycle
- Number of cycles will be categorized per below categories. Counts and percentages of participants in each of these categories will be summarized.
  - less than or equal to 1 cycle
  - at least 2 cycle, less than 4 cycles
  - at least 4 cycles, less than 6 cycles
  - 6 cycles or more
  - Unknown
- RDI will be categorized according to the following categories. Counts and percentages of participants in each of these categories will also be summarized.
  - less than 50%
  - at least 50%, less or equal to 80%
  - greater than 80%
  - Unknown

Duration of exposure (month) = (Last date of exposure – First dose date + 1)/30.4375.

For EV, last date of exposure = (date of initial dose of the last cycle + 28– 1) or death date if death occurred within the last cycle. For participants who are continuing study treatment at data cutoff date, data cutoff date will be used as the last date of exposure.

Number of cycles is the total number of cycles with non-zero dosing.

Cumulative dose is the sum of (total dose administrated) across all days.

Total dose administrated on a dosing day (mg) = final concentration (mg/ml) \* actual volume administrated (ml).

Planned dose intensity (mg/kg/cycle) is the initial dose of EV multiplied by planned number of dosing days per cycle.

For example, participant is planned to receive EV at a dose of 1.25mg/kg on days 1,8,15 of each cycle, the intended dose intensity =  $1.25 \text{ mg/kg} * 3 = 3.75 \text{ mg/kg}$  per cycle.

(Actual) Dose intensity (mg/kg/cycle) is defined as the actual dose of study drug per unit of time that a participant received over the entire treatment period, defined as below:

$$\text{Dose intensity} = \frac{\sum_{i=1}^{NC} \sum_{j=1}^3 (TD_{i,j} / W_{i,j})}{\text{Duration of exposure}/28}$$

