Where  $TD_{i,j}$  is the actual total drug administrated at cycle  $i$  day  $j$ ,  $W_{i,j}$  is the body weight of the participant at cycle  $i$  day 1, and  $NC$  is the total number of cycles with non-zero dosing. If the body weight is greater than 100kg, then  $W_{i,j} = 100\text{kg}$ . If there is no dose administrated in a planned dosing day in a cycle,  $TD_{i,j} = 0\text{mg}$ . Here the duration of exposure is in days.

For the purpose of computing actual, planned and relative dose intensity, neither death nor cutoff dates are used in the derivation of duration of exposure.

Relative dose intensity (%) is defined as

$$\frac{\text{Dose intensity}}{\text{Planned dose intensity}} \times 100$$

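### The TEAE event rate counts events to 30 days after last dose, but for participants off treatment its person-time stops on Day 28 of the last cycle

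*SAP*

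**What the plan says.** **Numerator.** SAP 4.5 defines a TEAE as an event that starts after the first administration of study drug and "within 30 days after taking the last dose of study drug". SAP 4.5.1 summarizes events on treatment and in the same 30 days. Neither section stops the count at new anticancer therapy.

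**Denominator.** SAP 4.5.1 gives the overview table a second time, as event counts and as the "number of events adjusted by patient year (defined as the total duration of exposure in years"). Duration of exposure is defined in SAP 4.2.11:

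- Off treatment: exposure ends 27 days after the first dose of the last cycle, which is Day 28 of that cycle, or on the "death date if death occurred within the last cycle".
- Still on treatment at data cutoff: the "data cutoff date will be used as the last date of exposure".

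Neither section adds the 30-day follow-up to the person-time.

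**The concern.** A rate per patient-year needs events and time at risk from the same period. Here the event window runs past the exposure window for many participants who have stopped treatment. Events in the uncovered days enter the numerator with no person-time behind them. Those days can hold serious events: Protocol 7.3.5 requires every death up to 30 days after the final dose to be reported as an SAE.

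The mismatch is also uneven. A participant still on treatment at cutoff has none, while one who has stopped usually has some. The reported rate therefore depends partly on how many participants have stopped by the cutoff. Protocol 2.1 describes the study as a bridge meant to show that safety is consistent with the non-Chinese population, so readers will look at descriptive safety rates.

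**Working it through.** The plan states no event rate, so there is no figure of its own to reproduce.

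**Inputs**

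- Dosing on Days 1, 8 and 15 of a 28-day cycle (Protocol 4.1).
- Visit window of ±3 days on Days 8 and 15, and at least 7 days between doses (Protocol Table 1 and its footnote n). A Day 15 dose can therefore fall on Day 18.
- Event window to last dose + 30 days (SAP 4.5).
- Exposure to Day 28 of the last cycle for participants off treatment (SAP 4.2.11).
- Anticipated treatment of about 8 months (Protocol 1.1). With the SAP's 30.4375 days per month, 8 × 30.4375 = 243.5 days.
- Three cycles, chosen to illustrate a shorter exposure: 3 × 28 = 84 days.

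**Gap in days.** If the last dose is on Day D of the last cycle, the event window closes on Day D + 30 and exposure on Day 28. Gap = (D + 30) − 28 = D + 2.

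**Relative size for one participant.** With the event count fixed, the rate on the SAP denominator divided by the rate on matched person-time is (T + gap)/T = 1 + gap/T, where T is exposure in days.

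| Last dose on | Window closes | Gap (days) | Gap/243.5 | Gap/84 |
|---|---|---|---|---|
| Day 1 | Day 31 | 3 | 1.2% | 3.6% |
| Day 8 | Day 38 | 10 | 4.1% | 11.9% |
| Day 15 | Day 45 | 17 | 7.0% | 20.2% |
| Day 18 | Day 48 | 20 | 8.2% | 23.8% |

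**Who has this gap.** The table holds for a participant who is off treatment, alive, before cutoff and without new anticancer therapy through last dose + 30 days. For others:

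- On treatment at cutoff: no gap, since exposure and events both end at cutoff.
- Death within the last cycle: no gap, since both end at death.
- Death after Day 28, or cutoff or new therapy between Day 28 and last dose + 30 days: a smaller gap.
- Cutoff before Day 28 in a participant who has already stopped: reversed. SAP 4.2.11 uses the cutoff date only for those continuing treatment. With cutoff on Day 20, exposure is still charged to Day 28, which is 28 − 20 = 8 days too many.
- New therapy before Day 28: reversed in the same way, if event collection stops there as in Protocol Table 1, footnote m.

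**Cohort.** The reported rate is total events over total exposure, so the overall overstatement is Σgap/ΣT. This is the exposure-weighted mean of the individual gap/T values, including zeros and negatives. Participants with short exposure have the largest gap/T and the least weight. Evaluating it needs the number off treatment, their last dosing days and their exposures, none of which the documents give.

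**The case against.** The strongest reply is that the denominator is openly defined, the study has one arm, and the rate is a secondary presentation of an overview table. The SOC and preferred-term tables count participants, so they do not use person-time. All of that stands, and it is why the point is minor. It does not make the two periods agree.

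It is also fair to say that stopping person-time at new anticancer therapy could create a fresh mismatch. Protocol Table 1, footnote m, ends AE collection at that point. Protocol 7.3.1 applies the stop to SAEs but collects all AEs until the follow-up visit. The SAP's TEAE definition has no such stop. If person-time ended at new therapy while events went on being counted, the same fault would return. The fix has to allow for this.

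A reader might infer that relative dose intensity in SAP 4.2.11 is defective too, because "neither death nor cutoff dates are used in the derivation of duration of exposure" there. A participant who receives the only dose due and dies on Days 1-7 of cycle 1 would show 1.25/3.75 = 33.3%. The documents do not support calling this an error. Charging 28 days for each dosed cycle is a stated convention that fits a planned intensity per cycle. SAP 5 shows that the duration rule was deliberate, although its reason concerns data cutoff and not death. Crediting only the doses due by death would leave the same effect for every other mid-cycle stop. With a visit-window allowance it could also hide a withheld dose. For example, if the Day 8 dose of cycle 4 is withheld and death follows on Day 10, before the window closes on Day 11, the result is 10/10 = 100%, against 10/12 = 83.3% under the current rule.

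**Conclusion.** The mismatch is real and minor. A participant off treatment whose full 30-day window is open contributes person-time that is 3, 10 or 17 days short at nominal dosing days, and up to 20 days short with the visit window. Relative to exposure this is 1.2% to 8.2% at 8 months and 3.6% to 23.8% at three cycles.

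These percentages rest on the anticipated 8-month duration and on three cycles taken as an illustration. They describe individual participants. A reader might take 23.8% as the error in the reported rate, or assume that the rate is always overstated. Neither follows: the gap is zero for some participants and can reverse for others, and the net cohort effect cannot be derived from the documents. Nor does the point reach the ORR test, the PK analyses or the participant-count AE tables. It concerns only the descriptive events-per-patient-year table.

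**What to change.** Add one sentence to SAP 4.5.1: for events per patient-year, person-time runs from first dose to the earliest of last dose + 30 days, death or data cutoff. This closes the gap of 3 to 20 days and removes the reversal when cutoff follows early after stopping. It changes nothing for participants on treatment at cutoff or who die within the last cycle.

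Decide whether start of new anticancer therapy ends the window. If it does, apply it to both the event count and the person-time. Protocol Table 1 footnote m, Protocol 7.3.1 and the TEAE definition in SAP 4.5 should be reconciled on this point first.

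Keep duration of exposure and relative dose intensity as SAP 4.2.11 defines them. The cost is the added SAP wording and reprogramming of one existing table, with no new data and no added analysis.
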